### **6.3.6 Other safety assessments**

Safety findings supporting the monitoring and evaluation of imAEs, including radiographic or pathologic findings, or pulmonary function tests (in case of pneumonitis or ILD), should be reported.

## **7 SAFETY REPORTING AND MEDICAL MANAGEMENT**

### **7.1 Definition of adverse events**

An AE is the development of an undesirable medical condition (other than progression of the malignancy under evaluation) or the deterioration of a pre-existing medical condition following or during exposure to a pharmaceutical product, whether or not considered causally related to the product. An undesirable medical condition can be symptoms (eg, nausea, chest pain), signs (eg, tachycardia, enlarged liver), or the abnormal results of an investigation (eg,

laboratory findings). In clinical studies, an AE can include an undesirable medical condition occurring at any time, including run-in or washout periods, even if no study treatment has been administered.

The term AE is used to include both SAEs and non-serious AEs.

## **7.2 Definitions of serious adverse event**

An SAE is an AE occurring during any study phase (ie, run-in, treatment, washout, follow-up), that fulfils one or more of the following criteria:

- results in death
- is immediately life-threatening
- requires in-patient hospitalization or prolongation of existing hospitalization
- results in persistent or significant disability/incapacity
- is a congenital abnormality or birth defect
- is an important medical event that may jeopardize the patient or may require medical intervention to prevent one of the outcomes listed above

All SAEs (ie, those occurring after the AE and SAE collection period) considered to be reasonably related to the study treatments or to the research must be notified to the sponsor with no time limit.

## **7.3 Collection of adverse events**

### **7.3.1 Time period for collection of adverse events**

Adverse events will be collected from time of signature of informed consent throughout the treatment period and including the follow-up period up to 90 days after the last dose of durvalumab treatment. If an event that starts post the defined safety follow up period noted above is considered to be due to a late onset toxicity to study drug then it should be reported as an AE or SAE as applicable.

All SAEs will be recorded and reported to the Sponsor or designee within 24 hours, as indicated in Appendix A. The Investigator will submit any updated SAE data to the Sponsor within 24 hours of it being available.

### **7.3.2 Follow-up of AEs and SAEs**

After the initial AE/SAE report, the Investigator is required to proactively follow each patient at subsequent visits/contacts. All AEs/SAEs will be followed until resolution, stabilization, the event is otherwise explained, or the patient is lost to follow-up.

Any AEs that are unresolved at the patient's last visit in the study are followed up by the Investigator for as long as medically indicated, but without further recording in the CRF. AstraZeneca retains the right to request additional information for any patient with ongoing AE(s)/SAE(s) at the end of the study, if judged necessary.

### **7.3.3 Adverse event data collection**

The following variables will be collected for each AE:

- AE (verbatim)
- The date when the AE started and stopped
- The maximum CTCAE grade reported
- Changes in CTCAE grade (report only the maximum CTCAE grade for a calendar day)
- Whether the AE is serious or not
- Investigator causality rating against the IPs (yes or no)
- Action taken with regard to IPs
- Administration of treatment for the AE
- Outcome

In addition, the following variables will be collected for SAEs:

- Date the AE met criteria for SAE
- Date the Investigator became aware of the SAE
- Seriousness criteria
- Date of hospitalization
- Date of discharge
- Probable cause of death
- Date of death
- Whether an autopsy was performed
- Causality assessment in relation to study procedure(s)
- Causality assessment in relation to other medication, as explained in Section 7.3.4
- Description of the SAE

The grading scales found in the revised NCI CTCAE version 5.0 will be utilized for all events with an assigned CTCAE grading. For those events without assigned CTCAE grades, the recommendation in the CTCAE criteria that converts mild, moderate, and severe events into CTCAE grades should be used. A copy of the CTCAE version 5.0 can be downloaded from the Cancer Therapy Evaluation Program website (<http://ctep.cancer.gov>).

It is important to distinguish between SAEs and severe AEs. Severity is a measure of intensity, whereas seriousness is defined by the criteria in Section 7.2. An AE of severe intensity need not necessarily be considered serious. For example, nausea that persists for several hours may be considered severe nausea, but it is not an SAE unless it meets the criteria shown in Section 7.2. On the other hand, a stroke that results in only a limited degree of disability may be considered a mild stroke, but it would be an SAE if it satisfies the criteria shown in Section 7.2.

#### **7.3.4 Causality collection**

The investigator will assess the causal relationship between the IPs and each AE and answer “yes” or “no” to the question “Do you consider that there is a reasonable possibility that the event may have been caused by the investigational product?”

For SAEs, causal relationship will also be assessed for other medications and study procedures. Note that, for SAEs that could be associated with any study procedure, the causal relationship is implied as “yes.”

#### **7.3.5 Adverse events based on signs and symptoms**

All AEs spontaneously reported by the patient or reported in response to questions from the study site staff, or revealed by observation will be collected and recorded in the CRF. When collecting AEs, the recording of diagnoses is preferred (when possible) to recording a list of signs and symptoms. However, if a diagnosis is known and there are other signs or symptoms that are not generally part of the diagnosis, the diagnosis and each sign or symptom will be recorded separately.

#### **7.3.6 Adverse events based on examinations and tests**

Deterioration as compared to baseline in protocol-mandated laboratory values should only be reported as AEs if they fulfil any of the SAE criteria or are the reason for discontinuation of treatment with the investigational product.

If deterioration in a laboratory value/vital sign is associated with clinical signs and symptoms, the sign or symptom will be reported as an AE and the associated laboratory result/vital sign will be considered as additional information. Wherever possible the reporting Investigator uses the clinical, rather than the laboratory term (eg, anemia versus low hemoglobin value). In the absence of clinical signs or symptoms, clinically relevant deteriorations in non-mandated parameters should be reported as AE(s).

Deterioration of a laboratory value, which is unequivocally due to disease progression, should not be reported as an AE/SAE.

Any new or aggravated clinically relevant abnormal medical finding at a physical examination as compared with the baseline assessment will be reported as an AE unless unequivocally related to the disease under study.

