Checkpoint inhibitors have been tested in SCLC, either used alone or in combination with chemotherapy. The IMpower133 study was presented at the World Congress on Lung Cancer (Horn et al 2018). IMpower133 was a randomized placebo-controlled phase III study, comparing atezolizumab + etoposide/carboplatin (EC) with placebo + EC in first line treatment of ES-SCLC. The study demonstrated a statistically significant improvement in OS with the combination of atezolizumab + etoposide/carboplatin compared to placebo + EC. Meanwhile, the CASPIAN study which was presented at the World Congress on Lung Cancer (Paz-Ares et al 2019) demonstrated a statistically significant improvement in OS of durvalumab plus etoposide/platinum (EP) compared to etoposide/platinum (EP) in first-line SCLC as well. CASPIAN was a randomised, open-label, phase 3 trial, to assess durvalumab, with or without tremelimumab, in combination with etoposide plus either cisplatin or carboplatin (EP) in treatment-naïve patients with ES-SCLC. CASPIAN met its primary endpoint of overall survival for durvalumab plus EP versus EP at the planned interim analysis, with a hazard ratio of 0.73 (95% CI 0.59–0.91;  $p=0.0047$ ); median overall survival was 13.0 months (95% CI 11.5–14.8) in the durvalumab plus EP group versus 10.3 months (9.3–11.2) in the EP group. Any-cause adverse events of grade 3 or 4 occurred in 163 (62%) of 265 treated patients in the durvalumab plus EP group and 166 (62%) of 266 in the EP group; adverse events leading to death occurred in 13 (5%) and 15 (6%) patients in the two groups, respectively. Immune-mediated adverse events (imAEs) were reported in 52 (20%) of 265 patients treated with durvalumab plus EP and seven (3%) of 266 patients treated with EP alone. Most of these events were grade 1 or 2; grade 3 or 4 imAEs occurred in 12 patients (5%) in the durvalumab plus EP group and one patient (<1%) in the EP group. Deaths due to imAEs occurred in one (<1%) patient in each group; causes of death were hepatotoxicity in

the durvalumab plus EP group and pneumonitis in the EP group. The most common imAEs were hypothyroid events (occurring in 24 [9%] patients in the durvalumab plus EP group and two [1%] patients in the EP group) and hyperthyroid events (occurring in 14 [5%] and none in the two groups, respectively), which were all grade 1 or 2 in severity.

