### 3 OBJECTIVES AND ENDPOINTS

All objectives will be evaluated for all patients, unless otherwise indicated.

| Primary objective:  | Endpoint/variable:                             |
|--|---|
| To assess the safety and tolerability of durvalumab + EP in patients with performance status 0-2 | Incidence of Grade $\geq 3$ AEs
Incidence of imAEs |

AE Adverse event; EP Etoposide and platinum-based chemotherapy; imAE Immune-mediated adverse event.

| Secondary objective:   | Endpoint/variable:  |
|---|--|
| To assess the efficacy of durvalumab + EP in patients with performance status 0-2 | PFS, APF12, ORR, DoR using site Investigator assessment and OS, OS12     |
| To further assess the safety and tolerability profile of durvalumab + EP          | Incidence of AEs, SAEs, AESIs, AE resulting in treatment discontinuation |

AESIs adverse event of special interest; DoR Duration of Response; EP Etoposide and platinum-based chemotherapy; ORR Objective response rate; OS Overall survival; OS12 Overall survival at 12 months after first dose of study treatment; PFS Progression free survival; APF12 Proportion of patients alive and progression free at 12 months after first dose of study treatment.

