## 6.3 Safety assessments

### 6.3.1 Clinical safety laboratory assessments

Blood and urine samples for determination of clinical chemistry, hematology, and urinalysis will be taken at the times indicated in the assessment schedules and as clinically indicated. Clinical laboratory safety tests, will be performed in a licensed clinical laboratory according to local standard procedures. Urine pregnancy tests may be performed at the site using a licensed test (urine or serum pregnancy test). Abnormal clinically significant laboratory results should be repeated as soon as possible (preferably within 24 to 48 hours).

Additional safety samples may be collected if clinically indicated at the discretion of the Investigator and according to standard medical practice. The date, time of collection, and results (values, units, and reference ranges) will be recorded. The Investigator should make an assessment of the available results with regard to clinically relevant abnormalities. The laboratory results should be signed and dated and retained at center as source data for laboratory variables. For information on how AEs based on laboratory tests should be recorded and reported, see Section 7.3.6.

Other safety tests to be performed at screening include assessment for hepatitis B surface antigen, hepatitis C antibodies and HIV antibodies. T-spot TB test will be performed when determined to be essential by investigator.

Sample tubes and sample sizes may vary depending on laboratory method used and routine practice at the site. Clinically significant (as assessed by the Investigator) laboratory abnormalities will be recorded as AEs. Laboratory results relevant to / associated with imAE will be recorded.

The laboratory variables to be measured are presented in Table 3 (clinical chemistry), Table 4 (hematology), and Table 5 (urinalysis).

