### 7.9.2 Chemotherapy

Chemotherapies are associated with a number of unwanted effects. EP-related toxicity management, dose adjustment, including dose delays and reductions should be performed as indicated in the local prescribing information for the relevant agent. In the event of unfavorable tolerability, patients can switch between cisplatin and carboplatin therapy at any point on study (assuming eligibility for the switched therapy is met).

EP is the SoC and is expected to cause hematologic non-immune-related AEs for which the non-immune-related Toxicity Management Guidelines should not be applied. Sites should utilize dose delays, dose modifications, G-CSF or component transfusions (eg, platelet transfusions) as necessary per local standards to maintain the dose and schedule of EP treatment to optimize tolerability for individual patients.

In the event that an AE can reasonably be attributed to EP, dose adjustment of EP should be attempted before modifying the administration of durvalumab.

In the event that EP is delayed, durvalumab should also be delayed and to be resumed as soon as feasible. Every effort should be made to ensure patients receive at least 4 cycles of EP, if conditions allow.

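### Sections 6.3.1 and 7.3.6 give incompatible rules for recording mandated-laboratory deteriorations as AEs, which leaves the primary Grade ≥3 AE count open to omission and to differences between sites

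*Protocol*

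**What the plan says.** Two sections of the protocol tell the site when a laboratory finding becomes an AE.

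- **Section 7.3.6**, on deterioration from baseline: "protocol-mandated laboratory values should only be reported as AEs if they fulfil any of the SAE criteria or are the reason for discontinuation" of study drug. The same section is wider for tests outside the schedule, where an asymptomatic change need only be clinically relevant to be reported.
- **Section 6.3.1**: "Clinically significant (as assessed by the Investigator) laboratory abnormalities will be recorded as AEs". No seriousness or discontinuation condition is attached.

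Section 6.3.1 also states: "For information on how AEs based on laboratory tests should be recorded and reported, see Section 7.3.6". The text after Table 5 points to 7.3.6 again. The general AE definition in Section 7.1 covers symptoms, signs "or the abnormal results of an investigation".

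The mandated panels in Tables 3 and 4 include neutrophils, platelets, hemoglobin, ALT, AST, bilirubin, amylase/lipase, creatinine and TSH. Section 3 names two primary endpoints: the incidence of Grade ≥3 AEs and "Incidence of imAEs". Section 9.5.1 analyses the first as the number and percentage of patients with such AEs, with Clopper-Pearson 95% intervals, and treats imAEs similarly.

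**The concern.** Take a non-serious, asymptomatic Grade 3 neutrophil count that the investigator considers clinically significant and that does not end treatment. It is an AE under 6.3.1 and not an AE under 7.3.6. Since the primary endpoint is built from recorded AEs, the two sections amount to two endpoint definitions.

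This class of event matters here. Section 7.9.2 states that "EP is the SoC and is expected to cause hematologic non-immune-related AEs", to be handled by dose delay, dose modification, G-CSF or transfusion. Delay, modification and G-CSF use are not in themselves exceptions under 7.3.6. The laboratory data that Section 9.4.1 assesses as a separate safety outcome do not feed the AE-based count. The safety review committee's look at the PS2 patients (Section 9.5.4) would share any gap in AE recording.

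**Working it through.** **1. The two rules side by side, for an abnormal value in a mandated test**

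| Type of finding | 6.3.1 | 7.3.6 |
|---|---|---|
| Meets an SAE criterion | AE | AE |
| Reason for stopping study drug | AE if clinically significant | AE |
| Accompanied by signs or symptoms | AE if clinically significant | the sign or symptom is the AE |
| Clinically significant, but asymptomatic, non-serious and not stopping treatment | AE | not an AE |

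The last row is the conflict. The cross-reference does not remove it. If 7.3.6 governs, practice is uniform but the last row is always omitted. If it does not, the last row is counted at some sites and not at others.

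**2. The plan's own precision (Section 9.2, Table 9)**

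Clopper-Pearson limits for x events in n patients: lower = Beta quantile 0.025 with parameters (x, n − x + 1); upper = Beta quantile 0.975 with parameters (x + 1, n − x). Precision is half the width.

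- Grade ≥3 AE at 60%: 180/300 gives 54.21% to 65.59%. Half-width (65.59 − 54.21)/2 = 5.69, against 5.7% stated.
- imAE at 20%: 60/300 gives 15.62% to 24.98%. Half-width (24.98 − 15.62)/2 = 4.68, against 4.7% stated.

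Both reproduce, as do all 15 cells of Table 9 after rounding.

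**3. Effect on the Grade ≥3 estimate if 7.3.6 is followed**

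Let s be the share of Grade ≥3 patients whose only qualifying events fall in the last row above. The protocol gives no value for s, so the values below are assumptions. Reported incidence = 60% × (1 − s). Coverage is the probability that the 95% interval from 300 patients contains the true 60%.

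| Assumed s | Reported | Bias (points) | 95% CI at the reported rate | Coverage of 60% |
|---|---|---|---|---|
| 5% | 57.0% | 3.0 | 51.2% to 62.7% | about 84% |
| 10% | 54.0% | 6.0 | 48.2% to 59.7% | about 48% |
| 20% | 48.0% | 12.0 | 42.2% to 53.8% | about 2% |

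The bias equals the planned half-width at s = 5.7/60 = 9.5%. A larger sample would not reduce it.

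**4. Mixed practice**

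If half the patients are at sites following each section, reported incidence = 60% × (1 − 0.5s): 57% for s = 10% and 54% for s = 20%.

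**5. imAEs, same formula from 20%**

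Losses of 5%, 10% and 20% give 19%, 18% and 16%. The bias reaches the 4.7-point half-width only at s = 4.7/20 = 23.5%.

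**The case against.** The best defence is that the protocol names a controlling section. Section 6.3.1 sends the reader to 7.3.6 twice, so divergent site practice is a risk and not an established fact. That stands. It only changes the form of the problem, because uniform use of 7.3.6 omits the same patients everywhere.

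The exceptions in 7.3.6 are also wider than they first look. Appendix A 5 lists blood dyscrasias such as neutropenia or anemia needing transfusion among examples of important medical events, Appendix B 5 makes Hy's law cases SAEs, and symptomatic deteriorations are reported through their symptoms. The endpoint is per patient, so any other Grade ≥3 AE keeps the patient in the count. These points limit the size of s but do not make it zero. Section 7.9.2 says that hematologic AEs are expected; it does not say how many are asymptomatic or non-serious.

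There is no hypothesis test, so no formal decision turns on the 60% or the 20%. That also stands. What is at stake is the accuracy of the estimate that the study exists to provide.

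Two stronger readings are tempting, and the protocol does not support them.

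- *A reader might infer that a large part of the imAE endpoint is lost.* Section 2.1.4 reports, for the cited phase III trial: "The most common imAEs were hypothyroid events (occurring in 24 [9%] patients in the durvalumab plus EP group", with 14 hyperthyroid patients, against 52 patients with any imAE. But it does not say how many of these were asymptomatic, untreated or known only from a laboratory value, and the two groups may overlap. Section 7.3.5 prefers diagnoses, 7.3.6 prefers clinical terms, and 7.5 names thyroid disorders, hepatitis and pancreatitis among AESIs/imAEs. A diagnosed hypothyroidism is reportable.
- *A reader might infer that both endpoints are certainly under-counted and cannot be compared with the cited trial's 62% and 20%.* Under-counting arises only where 7.3.6 is followed. The cited trial's own laboratory-reporting rule is not given, so its rates may rest on the same restriction or on a wider one.

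**Conclusion.** The contradiction is real and nothing elsewhere in the protocol resolves it. It bears mainly on the primary Grade ≥3 AE incidence: following 7.3.6 leaves out patients whose only Grade ≥3 event is an asymptomatic, non-serious, non-stopping value in a scheduled test, and mixed practice makes the figure site-dependent. The imAE incidence may be affected to a lesser degree.

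The size cannot be determined from the protocol. The 57%, 54% and 48% figures rest on a true incidence of 60%, 300 patients, every site following 7.3.6, and assumed laboratory-only shares of 5%, 10% and 20%. They show that a share of about 10% is enough for the bias to exceed the planned precision. They do not show that the share is that large.

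**What to change.** 1. Replace the first sentence of Section 7.3.6 with one rule consistent with 6.3.1: a deterioration in a mandated laboratory value is recorded as an AE if the investigator judges it clinically significant, if it meets an SAE criterion, or if it leads to discontinuation of study drug. No further triggers are needed to make the two sections agree. Narrowing 6.3.1 to match 7.3.6 instead would also remove the contradiction, but it would keep the omission.
2. Notify sites of the single rule and the date from which it applies.
3. Add a supportive Grade ≥3 incidence in which a patient counts if there is a recorded Grade ≥3 AE or a post-baseline laboratory value of CTCAE Grade ≥3. This covers patients enrolled under the present wording. Section 6.3.1 already requires results, units and reference ranges to be recorded. The sponsor should confirm that all scheduled results reach the database.

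The cost is a wording change, a site notice, more AE entries and one extra table. The reported Grade ≥3 incidence may come out higher.

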## 7.5 Adverse events of special interest

An adverse event of special interest (AESI) is one of scientific and medical interest specific to understanding of the Investigational Product and may require close monitoring and rapid communication by the investigator to the sponsor. An AESI may be serious or non-serious. The rapid reporting of AESIs allows ongoing surveillance of these events in order to characterize and understand them in association with the use of this investigational product.

AESIs for durvalumab include but are not limited to events with a potential inflammatory or immune-mediated mechanism and which may require more frequent monitoring and/or interventions such as steroids, immunosuppressants and/or hormone replacement therapy. These AESIs are being closely monitored in clinical studies with durvalumab monotherapy and combination therapy. An immune-mediated adverse event (imAE) is defined as an AESI that is associated with drug exposure and is consistent with an immune-mediated mechanism of action and where there is no clear alternate aetiology. Serologic, immunologic, and histologic (biopsy) data, as appropriate, should be used to support an imAE diagnosis. Appropriate efforts should be made to rule out neoplastic, infectious, metabolic, toxin, or other etiologic causes of the imAE.

AESI/imAEs observed with anti PD-L/PD-1 agents such as durvalumab include pneumonitis, hepatitis, diarrhea/colitis, intestinal perforation, endocrinopathies (hypo- and hyper-thyroidism, adrenal insufficiency, hypophysitis/hypopituitarism and Type 1 diabetes mellitus), nephritis, rash/dermatitis, myocarditis, myositis/polymyositis, pancreatitis and rare/less frequent imAEs including neuromuscular toxicities such as myasthenia gravis and Guillain-Barre syndrome.

Other inflammatory responses that are rare/less frequent with a potential immune-mediated etiology include, but are not limited to, pericarditis, sarcoidosis, uveitis, and other events involving the eye, skin, hematological, rheumatological events, vasculitis, non-infectious meningitis and non-infectious encephalitis. It is possible that events with an inflammatory or immune mediated mechanism could occur in nearly all organs

In addition, infusion-related reactions and hypersensitivity/anaphylactic reactions with a different underlying pharmacological etiology are also considered AESIs.

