#### **Adverse events**

Adverse events will be summarized as follows in terms of both Medical Dictionary for Regulatory Activities [MedDRA] preferred terms and CTCAE grade:

**AE:** Number and proportion of patients with AEs in total and by causality and severity

**AE with Grade  $\geq 3$ :** Number and proportion of patients with Grade  $\geq 3$  AEs

**SAE:** Number and proportion of patients with SAEs in total and by causality and severity

**AEs leading to death:** Number and proportion of patients with AEs leading to death

**AEs leading to treatment discontinuation:** Number and proportion of patients with AEs leading to treatment discontinuation

**AESIs:** An adverse event of special interest (AESI) is one of scientific and medical interest specific to understanding of the Investigational Product and may require close monitoring and rapid communication by the investigator to the sponsor. An AESI may be serious or non-serious. Please refer to Section 7.5. In order to further characterize safety objectives related to AESIs, outcome measures will be assessed, which may include (and are not necessarily limited to) the following:

- (a) Number and proportion of patients with AESIs, by pre-defined type (or newly defined by this study) in total and by seriousness, severity and causality, including immune-relatedness;
- (b) Number and proportion of patients who received steroids, immunosuppressants and/or hormone replacement therapy to manage AESIs;
- (c) Time from start of durvalumab (MEDI4736) to the onset of an AESI pre-defined type, all

interventions of AESIs by type of intervention (including intervention with steroids, immunosuppressants and/or hormone replacement therapy), and time from onset of an AESI type to resolution;

(d) Duration of the intervention with steroids, immunosuppressants and/or hormone replacement therapy until the resolution of AESI;

(e) Laboratory findings, vital signs and other safety parameters associated with AESIs will be summarized as part of the AESI outcome measures.

**imAEs:** The imAEs will be assessed as a subset of AESIs. Please refer to Section 7.5.

Any AE occurring before treatment with study drug will be included in the data listings but will not be included in the summary tables of AEs. Any AE occurring within 90 days of discontinuation of durvalumab will be included in the AE summaries.

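### Section 7.3.6 can put a Grade ≥3 laboratory toxicity on record only as a milder symptom, in conflict with Section 6.3.1, so the primary Grade ≥3 AE incidence can be understated and can vary by site

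*Protocol*

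**What the plan says.** Three protocol sections govern how a laboratory finding becomes an AE.

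- **Section 7.3.6, opening sentence.** Deteriorations in protocol-mandated laboratory values "should only be reported as AEs if they fulfil any of the SAE criteria or are the reason for discontinuation" of study treatment.
- **Section 7.3.6, second paragraph.** If the deterioration comes with clinical signs or symptoms, "the sign or symptom will be reported as an AE and the associated laboratory result/vital sign will be considered as additional information". The next sentence adds: "Wherever possible the reporting Investigator uses the clinical, rather than the laboratory term (eg, anemia versus low hemoglobin value").
- **Section 6.3.1.** "Clinically significant (as assessed by the Investigator) laboratory abnormalities will be recorded as AEs", with no condition about symptoms, seriousness or discontinuation. The same section sends the reader to 7.3.6 for how laboratory-based AEs are recorded.
- **Section 7.3.5.** When AEs are collected, "the recording of diagnoses is preferred (when possible) to recording a list of signs and symptoms".

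Section 7.3.3 collects the maximum CTCAE grade of each AE as entered, using version 5.0. Section 9.5.1 counts patients with an AE of Grade 3 or above as one primary measure and analyses immune-mediated AEs (imAEs) in a similar way. Section 9.4.1 states: "The imAEs will be assessed as a subset of AESIs".

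**The concern.** The first primary endpoint is a count of patients by AE grade, so the rule that decides which term is entered also decides the grade that is counted. Take an ALT rise in the Grade 3 range with mild nausea and no diagnosis of hepatitis. Under the symptom rule of 7.3.6 the AE is nausea at a low grade, and the ALT value is supporting information. Under 6.3.1, if the investigator judges the rise clinically significant, it is an AE with its own grade. Section 7.3.6 does not refer back to 7.3.5, and it does not say whether the laboratory grade or the symptom grade is the grade of the AE.

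Two sites following the protocol in good faith can therefore enter the same patient differently, and a patient with symptoms can be counted as less severe than the laboratory value shows. Term and grade choices are hard to reconstruct once the data have been entered.

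**Working it through.** **Step 1. Does the literal text lose the laboratory grade?** The case is a protocol-mandated test at Grade ≥3 with a mild symptom, no named diagnosis, not serious, treatment continued. Tables 2 to 4 cover the likely tests: ALT, AST, creatinine, amylase or lipase, glucose, thyroid-stimulating hormone and blood counts.

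| Rule | AE entered | Grade counted |
|---|---|---|
| 7.3.6, opening sentence | No separate laboratory AE | None |
| 7.3.6, symptom rule | The symptom | The symptom's grade |
| 7.3.6, clinical-term sentence | Helps only if the finding has a clinical name | None assigned by this sentence |
| 6.3.1 | The laboratory abnormality, if judged clinically significant | The laboratory grade |
| 7.3.5 | No diagnosis to prefer; no grading rule | None |

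Under 7.3.6 alone no Grade ≥3 AE is entered for this event. Under 6.3.1 one is. The value stays in the laboratory data that Section 9.4.1 also lists, but the primary endpoint counts AEs.

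**Step 2. Reproduce the stated precision (Section 9.2 and Table 9).** The Clopper-Pearson 95% limits for x events in n patients are:

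- lower = Beta quantile at 0.025 with parameters (x, n − x + 1)
- upper = Beta quantile at 0.975 with parameters (x + 1, n − x)
- precision = (upper − lower)/2

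Results:

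- Grade ≥3 AE, 60% of 300: x = 180, interval 54.2% to 65.6%, half-width 5.69 points (stated 5.7%).
- imAE, 20% of 300: x = 60, interval 15.6% to 25.0%, half-width 4.68 points (stated 4.7%).

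All 15 cells of Table 9 reproduce to one decimal. The precision figures are correct and this point does not change them.

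**Step 3. Sensitivity of the Grade ≥3 incidence.** Let m be the share of patients with a true Grade ≥3 event who end up with no Grade ≥3 AE on record. Recorded incidence = 60% × (1 − m). The documents give no value for m, so these are assumptions.

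| m | Patients recorded | Recorded incidence (95% CI) | Shift |
|---|---|---|---|
| 5% | 180 × 0.95 = 171 | 57.0% (51.2 to 62.7) | 3.0 points |
| 10% | 180 × 0.90 = 162 | 54.0% (48.2 to 59.7) | 6.0 points |
| 20% | 180 × 0.80 = 144 | 48.0% (42.2 to 53.8) | 12.0 points |

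The shift reaches the stated precision when m = 5.7/60 = 9.5%.

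**Step 4. The same shares for imAEs.** Recorded incidence = 20% × (1 − m), giving 19%, 18% and 16%. The shifts of 1, 2 and 4 points are all smaller than the 4.7-point precision.

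**The case against.** The strongest reply is that 7.3.5 and 7.3.6 answer different questions. The former chooses between a diagnosis and a list of symptoms, the latter between a laboratory number and its clinical manifestation. Read together, they ask for the clinical event, under its diagnosis where there is one. The example in 7.3.6, anemia, is a diagnosis-type term and fits that reading. This stands. A reader might infer that 7.3.6 flatly overrides the diagnosis preference, but nothing in it forbids a diagnosis. What the reply leaves open is the toxicity without a clinical name, the grade to apply, and the conflict with 6.3.1.

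A reader might also infer that imAEs are systematically lost, for example hypothyroidism entered as fatigue. Section 7.5 does list diagnoses that rest largely on laboratory tests, such as "endocrinopathies (hypo- and hyper-thyroidism, adrenal insufficiency, hypophysitis/hypopituitarism and Type 1 diabetes mellitus), nephritis, rash/dermatitis". In the randomised phase 3 trial described in Section 2.1.4, 24 of 52 imAE patients (46%) had hypothyroid events and 14 had hyperthyroid events, at most 38 of 52 (73%) together. The documents do not support the inference, for these reasons:

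- Those categories have clinical names, which the clinical-term sentence favours.
- Section 6.3.1 says "Laboratory results relevant to / associated with imAE will be recorded". Section 7.5 asks for supporting data towards an imAE diagnosis, and Sections 7.9 and 7.9.1 treat events without a clear alternative cause as potentially immune related.
- A patient leaves the imAE count only if no other imAE is recorded.
- The thyroid events cited were all Grade 1 or 2, so they say nothing about the Grade ≥3 endpoint.

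These provisions do not spell out which AE term to enter, so the imAE risk is reduced but not closed.

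Finally, the endpoint is per patient. A downgraded event changes the count only if the patient has no other Grade ≥3 AE. This stands and limits the size. Completion guidelines for the case report form, which are not shown, could settle the term and grade, but they should not have to choose between two conflicting protocol sections.

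**Conclusion.** The point holds for the Grade ≥3 endpoint. As written, 7.3.6 can lead to a Grade ≥3 laboratory toxicity being entered only at a symptom's lower grade, and 6.3.1 states a different rule. The direction is towards understatement, with variation between sites. This rests on a literal reading of 7.3.6 and on three conditions: no named diagnosis or clinical term, an event that is neither serious nor a reason for stopping treatment, and no other Grade ≥3 AE in the same patient.

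The true size is unknown. On assumed losses of 5% to 10% of true cases the shift is 3 to 6 points, and it passes the 5.7-point precision at about 9.5%. That shows scale only and is not evidence that such losses will occur. For imAEs the effect is possible but less certain, and no bias can be claimed from the documents. The sample size rationale is unaffected. The sections should be reconciled because a stated recording rule, and not merely a missing detail, can lower a primary count.

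**What to change.** Amend Section 7.3.6 and bring 6.3.1 and 7.3.5 into line with it:

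1. Where a diagnosis or clinical term exists (for example hypothyroidism, hepatitis or anemia), record it as the AE with its CTCAE v5.0 grade, using laboratory-based grading where CTCAE defines it.
2. Where none exists, record a clinically significant laboratory toxicity as its own AE with its own CTCAE grade, in addition to the symptom.
3. Change the opening sentence of 7.3.6 so that it allows step 2, and use the same criterion in 6.3.1. If only the symptom sentence is replaced, the opening sentence will contradict the new rule.
4. Add a cross-reference from 7.3.6 to 7.3.5, and repeat the rule in the case report form completion guidelines.

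The cost is a short amendment, some additional AE entries and a slightly higher reported Grade ≥3 incidence. Data already entered under the present wording would need a check of Grade ≥3 laboratory values against the AE records.
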